9.2.2. Exclusion Criteria

Patients meeting any of the following criteria will not be included in the study:

1. Patients taking tofacitinib in combination with any other bDMARD

9.3. Variables

Patient characteristics at baseline:

- Gender, age, race, and ethnicity;
- Duration of PsA (Age at onset);
- Time since PsA diagnosis
- Time since onset of PsO;
- Comorbidity history:
 - Cardiovascular disease: MI, stroke, TIA acute coronary syndrome, coronary artery disease, CHF, revascularization procedure including percutaneous coronary intervention [PCI], coronary artery bypass grafting [CABG] or coronary artery stents, ventricular arrhythmia, cardiac arrest, unstable angina, other CV diseases, carotid artery disease, other coronary disease, peripheral arterial disease);
 - Hypertension;
 - Hyperlipidemia;
 - Serious infections;
 - Malignancy: lung cancer, breast cancer, lymphoma, skin cancer (melanoma and not melanoma), and other cancer;

- Thromboembolic events (Deep vein thrombosis, peripheral arterial thromboembolic and pulmonary embolism);
- Anxiety, depression, and other mood disorders;
- Crohn's Disease;
- Psoriasis;
- Diabetes;
- Ulcerative colitis;
- Uveitis;
- Metabolic Syndrome;
- Psoriatic Nail Dystrophy;
- Fibromyalgia.
- Smoking status;
- Alcohol use;
- Work status;
- Height and weight;
- Insurance (patient reported);
- Prior small molecule (SM) use;
- Prior biologic use:
 - Prior TNFi use;
 - Prior non-TNFi use.
- Current prednisone use (including dose).

Disease activity measures:

- Physician reported:
 - Tender Joint Count (28 and 68);

PFIZER CONFIDENTIAL

CT24-WI-GL02-RF02 4.0 Non-Interventional Study Protocol Template For Secondary Data Collection Study
01-Jun-2022
Page 13 of 19

- Swollen Joint Count (28 and 66);
- SPARCC count;
- Enthesitis;
- Dactylitis;
- LEI count;
- Dactylitis count;
- MDA;
- DAPSA;
- PASDAS;
- ACR20/50/70;
- mACR20/50/70;
- Nail VAS;
- BSA;
- CRP;
- Spinal mobility measures (occiput to wall distance, left and right lateral lumbar flexion, modified Schober);
- Global assessment of PsO.
- Patient reported:
 - Pain (VAS);
 - Fatigue (VAS);
 - Global Skin Assessment;
 - HAQ-DI;
 - HAQ-S;
 - European Quality of Life-5 Dimensions (EQ-5D-5L);

- WPAI domains (4 categories).

9.4. Data Sources

Patients are enrolled in the CorEvitas PsA/SpA Registry during regularly-scheduled office visits. Upon enrollment, providers complete a set of Enrollment Questionnaires on PsA patients. Patients also complete an Enrollment Questionnaire, which captures several data elements, including the Health Assessment Questionnaire (HAQ) and the European Quality of Life-5 Dimensions (EQ-5D-5L). Both patient and provider reported disease activity measures obtained at each visit are captured in CorEvitas; this includes tender and swollen joint counts (28 and 66/68 joint counts), patient and physician global disease assessment, patient pain assessment and HAQ scores. Providers and patients complete Follow-Up Questionnaires approximately every 6 months. During the course of a regularly-scheduled office visit, the provider performs assessments as mandated on the CorEvitas Provider Questionnaires with recording of pertinent data. Results from certain laboratory tests are included, but not mandated. Likewise, during regularly-scheduled office visits, patients are asked to complete Questionnaires designed to capture information ranging from their general demographics and experience with prescription drug use to an overall global assessment of their disease. Early follow-up visits occur and questionnaires are completed whenever a registry patient is being prescribed or receiving a first dose of a new (different) eligible medication at a regularly-scheduled office visit. Eligible medications are biologics, biosimilars, and JAK inhibitors FDA-approved for the treatment of PsA. The next regularly-scheduled visit is calculated from the previous visit. Data are collected on patients for as long as they consent to remain in the registry.

9.5. Study Size

This is an estimation study and not hypothesis testing study. Precision estimates indicate that approximately 80-73 patients with 12 months of follow-up are needed per group to achieve reasonably precise estimates for the outcomes of interest. For binomial proportions, a sample size of 80-73 patients per group would yield a half width of the 2-sided 95% confidence interval (CI) to be less than 11 percentage points for the binomial proportions, and less than 16 percentage points for the difference in 2 binomial proportions.

As of October 1, 2020, there are 160 tofacitinib initiators within the CorEvitas registry of whom 93 have a 6 month follow-up visit. The first objective of the study will be assessed using the latest data cut available once the protocol is approved and will be reported in the first interim report. The stratifications by mono and combination therapy listed in the second objective will be reported in subsequent interim reports as sample sizes reach appropriate thresholds. For comparative analyses, this will be at least 80-73 patients per arm. Precision estimates will be used to determine appropriate sample sizes for the descriptive analyses. The final report will be issued once all subgroups reach the minimal sample sizes to ensure sufficient precision in the estimates of the outcomes.

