5. AMENDMENTS AND UPDATES

Amendment number	Date	Protocol section(s) changed	Summary of amendment(s)	Reason
1	24May2023	9.3	Administrative change regarding CDAI and cDAPSA values	The values for CDAI and cDAPSA are being pulled from the database. Pfizer will not do any recalculation post-hoc
1	24May2023	9.5	Planned sample size reduced from 100 to 80 patients per group Substantial Amendment	Based on CorEvitas estimates and current enrollment pattern, it is estimated that it will take approximately 12 months to get to at least 80 patients per group.
1	24 May 2023	3	Adding Author (PPD) address and new PPD PPD	NY Pfizer offices changed
1	24 May 2023	6	Interim report 3, end of data collection, and final study report dates were updated	Update due to the amendment
2	02Oct2023	9.5	Planned sample size reduced from 80 to 73 patients per group Substantial Amendment	Based on CorEvitas estimates and current enrollment pattern, it is estimated that it will take approximately 12 months to get to at least 73 patients per group.

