9.7. Data Analysis

Detailed methodology for summary and statistical analyses of data collected in this study will be documented in a statistical analysis plan (SAP), which will be dated, filed and maintained by the sponsor. The SAP may modify the plans outlined in the protocol; any major modifications of endpoint definitions or their analyses would be reflected in a protocol amendment.

In general, the data for all continuous endpoints will be summarized by timepoint and treatment group in tables containing descriptive statistics (N, mean, standard deviation, standard error of the mean, minimum, 1st, 2nd (ie, median) and 3rd quartiles and maximum) for baseline and change from baseline/percent change from baseline for those endpoints measured at baseline. The data for all categorical endpoints will be summarized by contingency tables that show the counts/frequency in the various categories by treatment group at each timepoint.

For binary endpoints, 95% CI using normal approximation to binomial proportions will be provided for each group. The 95% CI will also be provided for comparisons between groups using normal approximation for the difference in binomial proportions.

Continuous endpoints (eg, HAQ-DI) at month 6 will be analyzed as change from baseline with an analysis of covariance (ANCOVA) model that includes treatment and baseline value as covariates. Comparisons between groups will be performed using 95% CI.

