At the six-month follow-up visit, the following will be assessed:

Among those not in the specified disease activity state, achievement of:

- Minimal Disease Activity
- Body Surface Area Score of 0
- PASDAS < 3.2
- Resolution of enthesitis
- Resolution of dactylitis
- Clinical Global Assessment of PsO – achievement of “Clear” or “Almost Clear”

Baseline to six months change in:

- cDAPSA
- DAPSA
- PASDAS
- HAQ-DI
- Low Disease Activity as defined by cDAPSA (cDAPSA ≤ 13)
- BSA
- CDAI
- Tender joint count (68)
- Swollen joint count (66)
- Patient global skin assessment
- Patient pain
- Patient fatigue
- Clinical Global Assessment of PsO
- WPAI Domains

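### At the current 73 patients per group, the protocol's stated confidence-interval half-widths (under 11 points for a rate, under 16 for a difference) are not met; the worst-case values are 11.5 and 16.2.

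*Protocol*

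**What the plan says.** Protocol section 9.5 presents the study as one of estimation and rests its size on the half-width of the two-sided 95% CI. It says the planned number per group gives half-widths "less than 11 percentage points for the binomial proportions, and less than 16 percentage points for the difference in 2 binomial proportions". No response rate is attached to these limits.

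The current number is 73. The entry for amendment 2 in section 5 reads "Planned sample size reduced from 80 to 73 patients per group" and gives the enrolment pattern as the reason. In the text available to us, section 9.5 prints both values together, for example "For comparative analyses, this will be at least 80-73 patients per arm".

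The interval method is fixed in section 9.7: "For binary endpoints, 95% CI using normal approximation to binomial proportions will be provided for each group", and for "comparisons between groups using normal approximation for the difference in binomial proportions". The SAP (Milestone 2) repeats this.

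The SAP's list of six-month outcomes introduces six binary endpoints with "Among those not in the specified disease activity state, achievement of": minimal disease activity, BSA of 0, PASDAS below 3.2, resolution of enthesitis, resolution of dactylitis, and a clear or almost clear global assessment of psoriasis. Table 6 of the SAP has seven binary outcomes. The seventh, low disease activity by cDAPSA, is not under that restriction.

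**The concern.** The limits of 11 and 16 points look like figures worked out for 80 per group and left in place when the number fell to 73. A half-width limit stated without a response rate has to hold at the least favourable rate, 50%, and 73 patients appear too few for that.

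In an estimation study the precision statement is the only quantitative support for the sample size. Section 9.5 also ties the final report to sizes that give sufficient precision. If the figures are wrong, the protocol claims a property that the design does not have, and a substantial amendment changed the number without updating its justification.

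A second point adds to this. Patients already in the target state at baseline leave the denominator for most binary outcomes, so a precision statement for the full group would not describe those outcomes at any group size.

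**Working it through.** **Inputs.** Group size 73, previously 80 (protocol sections 5 and 9.5). Two-sided 95% interval, z = 1.95996 (section 9.5). Normal approximation for a rate and for a difference (section 9.7; SAP, Milestone 2). Rate p = 0.5, because no rate is stated and this gives the widest interval. Equal groups for the difference.

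**Formulas.** One rate: h1 = z × √(p(1−p)/n). Difference with a common rate: h2 = z × √(2p(1−p)/n).

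**Reproducing the stated limits, n = 80, p = 0.5**

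- h1 = 1.95996 × √(0.25/80) = 10.96 points, under 11.
- h2 = 1.95996 × √(0.5/80) = 15.49 points, under 16.

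**Current size, n = 73, p = 0.5**

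- h1 = 1.95996 × √(0.25/73) = 11.47 points, not under 11.
- h2 = 1.95996 × √(0.5/73) = 16.22 points, not under 16.

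**Smallest n that meets each limit at p = 0.5**

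- Under 11: 0.25 × (1.95996/0.11)² = 79.4, so 80 per group.
- Under 16: 0.5 × (1.95996/0.16)² = 75.03, so 76 per group.

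The first minimum is exactly the superseded number.

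**Rates for which the limits do hold at n = 73**

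- Under 11: p(1−p) < 73 × (0.11/1.95996)² = 0.2299, so p below 35.8% or above 64.2%.
- Under 16, common rate: p(1−p) < (73/2) × (0.16/1.95996)² = 0.2432, so p below 41.8% or above 58.2%.

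**Other interval methods at n = 73 and a rate of 50%** (the exact interval uses 36 of 73)

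| Method | Rate | Difference |
|---|---|---|
| Planned normal approximation | 11.47 | 16.22 |
| With continuity correction | 12.15 | 17.59 |
| Wilson / Newcombe | 11.18 | 15.81 |
| Clopper-Pearson | 11.94 | – |

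No 95% method tried brings the single rate under 11. Newcombe brings the difference under 16, but it is not the planned method.

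**Outcomes restricted to a baseline subset.** The documents give no baseline prevalence for any target state, so the evaluable shares below are assumptions (p = 0.5, n rounded).

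| Assumed share of 73 | n | Rate | Difference |
|---|---|---|---|
| 90% | 66 | 12.1 | 17.1 |
| 75% | 55 | 13.2 | 18.7 |
| 50% | 36 | 16.3 | 23.1 |
| 20% | 15 | 25.3 | 35.8 |

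Non-response imputation (SAP, Milestone 2) keeps patients with missing six-month values in the denominator. It does not bring back those excluded for their baseline state.

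**The case against.** The strongest reply is that the miss is trivial. It is 0.47 and 0.22 points, in a section that calls its numbers approximate and its precision reasonable. No analysis changes, and the reported intervals will show the precision actually achieved. The comparative analyses are also triggered by a patient count, so correcting the half-widths would not move that trigger. All of this is true. It limits the consequence of the error but does not make the stated figures correct.

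The difference limit is also fragile in the plan's favour. Section 9.5 sets 73 as a minimum per arm, so one arm will probably be larger. The SAP's feasibility table shows 59 and 55 patients with a six-month visit. If that ratio held, 73 in the smaller arm would go with 73 × 59/55 ≈ 78 in the larger, and 1.95996 × √(0.25/73 + 0.25/78) = 15.96 points, just under 16. Unequal rates such as 50% and 38% at 73 per arm give 15.99. These rescues stand only under assumptions that the protocol does not make, and neither helps the single-rate limit in a group of 73.

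The subset point would apply equally at 80 or 100 per group, and its size rests on assumed shares. Both remarks are fair. The direction is still certain: excluding patients can only shrink the denominator, which widens the interval at a given rate.

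The SAP (Milestone 2) still makes the stratified analyses wait for 100 initiators per group, where the half-widths would be 9.80 and 13.86. That does not make the protocol's statement true for 73; it is a further mismatch between the two documents. Finally, the paired 80-73 may be a tracked change whose strike-through was lost in the text available to us. The finding does not depend on it.

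**Conclusion.** The concern holds. With the planned method and no stated rate, 73 per group gives worst-case half-widths of 11.47 and 16.22 points, so both limits in section 9.5 are wrong as written. They fit the superseded 80, which indicates that they were carried over.

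For outcomes that use the whole group the shortfall is about half a point or less and is confined to mid-range rates. The result for the difference assumes equal arms and a common rate near 50%; the result for a single rate assumes only a rate between about 35.8% and 64.2%. For the six restricted outcomes the stated precision does not apply as a general property. The loss there could be much larger, but it cannot be quantified from the documents.

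**What to change.** In protocol section 9.5, restate the precision for 73 evaluable patients per group: a half-width under 12 points for a rate and under 17 points for a difference, both at a rate of 50%. Alternatively, keep 11 and 16 and state where they hold: rates below 35.8% or above 64.2% for a single proportion, and a common rate below 41.8% or above 58.2% for a difference between equal groups.

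Add a sentence saying that outcomes limited to patients not in the target state at baseline have the precision of their own denominator, with an example at an assumed evaluable share. At 50% of 73 (n = 36) this would be 16.3 and 23.1 points. If the issued protocol really prints both 80 and 73, leave only the current number.

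The cost is a short edit to section 9.5 and slightly less favourable figures. No extra patients and no change of analysis are needed. The SAP's trigger of 100 per group should be reconciled with the protocol's 73 as a separate edit.

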6. MILESTONES

Milestone	Planned date*
Start of data collection	15 November 2021
Interim Report 1	15 January 2022
Interim Report 2	19 December 2022
Interim Report 3	15 Sep 2023
End of data collection	29 March 2024
Final study report	28 June 2024

*The interim reports rely on reaching the appropriate number of patients for each analysis. These dates may change if there are delays in patient accrual within the registry.

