8. RESEARCH QUESTION AND OBJECTIVES

There are two primary objectives for this study:

1. To describe the effectiveness of all tofacitinib initiators at 6 months in PsA patients.
2. To describe the effectiveness of all tofacitinib initiators at 6 months stratified by mono- and combination therapy of PsA.

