#### **Analysis:**

##### **Milestone 1:**

Consider the demographic, patient, and disease characteristics of all eligible tofacitinib initiators in **Table 1**. Categorical variables will be examined using frequencies and proportions. Continuous variables will be summarized using descriptive statistics (mean, standard deviation, minimum, 25% percentile, median, 75% percentile, maximum).

In **Table 2**, we will present the therapy status of initiators at the six-month follow-up visit.

**Table 3** will examine the outcomes of interest at the six-month follow-up visit. Binary outcomes will be presented as response rates with 95% CI using normal approximation to binomial proportions, and summary statistics (n, mean (SD), [P0,P25,P50,P75,P100]) baseline, six-month, and change in continuous outcomes will also be presented.

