### Milestone 2:

The analyses stratified by mono- and combination therapy for this milestone will be completed when the sample reaches at least 100 initiators in both mono- and combination therapy groups.

Consider the demographic, patient, and disease characteristics of the tofacitinib monotherapy and combination therapy initiators in **Table 4**. Categorical variables will be examined using frequencies and proportions, and, when sample size allows for significance testing, differences across therapy patterns will be tested using chi-square or Fisher exact tests. Continuous variables will be summarized using descriptive statistics (n, mean, standard deviation, minimum, 25% percentile, median, 75% percentile, maximum). When sample size allows for significance testing, differences across therapy groups will be tested using Wilcoxon rank sum tests.

In **Table 5**, we will present the therapy status of initiators at the six-month follow-up visit.

**Table 6** will examine the outcomes of interest at the six-month follow-up visit. The change from baseline to six months in continuous outcomes will be analyzed using an analysis of covariance model with fixed effects for treatment group and baseline value. For continuous outcomes, we will not impute missing values. Also, for those discontinuing therapy prior to follow-up, we will use the value immediately prior to discontinuation as the follow-up value. We will present LS Means (standard error) for each therapy group as well as the difference in the LS Means (standard error), 95% CI and p-value. Binary outcomes will be presented as response rates with 95% CIs using normal approximation to binomial proportions. We will provide comparisons of response rates between groups with 95% CIs and p-values using normal approximation for the difference in binomial proportions. As a supportive analysis, treatment difference between the groups will be assessed using logistic regression models with treatment group as the sole covariate. For binary outcomes, we will impute non-response for missing values and for those patients discontinuing therapy prior to follow-up.

In **Table 7**, we will present summary statistics (n, mean (SD), [P0,P25,P50,P75,P100]) for continuous outcomes featured in Table 3 at baseline, six months, and the difference from baseline to six months overall and by therapy group.

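### No re-estimation of the overall binary response rates is planned on the later, larger cohort, although the overall baseline, therapy-status and continuous results are refreshed at Milestone 2

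*Protocol*

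**What the plan says.** Protocol section 8 lists two primary objectives. The first is: "To describe the effectiveness of all tofacitinib initiators at 6 months in PsA patients". The second asks the same question by monotherapy and combination therapy.

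Protocol 9.5 fixes when each is answered. For objective 1 it says: "The first objective of the study will be assessed using the latest data cut available once the protocol is approved and will be reported in" Interim Report 1. The strata follow in subsequent interim reports as their sizes allow; for comparative analyses, "this will be at least 80-73 patients per arm" (amendment 2 moves the figure from 80 to 73). The final report is triggered by subgroup size. Its contents are not described. Section 6 plans Interim Report 1 for "15 January 2022" and the end of data collection for 29 March 2024, about 26 months later.

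In the SAP, under Milestone 1, Table 3 "will examine the outcomes of interest at the six-month follow-up visit. Binary outcomes will be presented as response rates with 95% CI" for all initiators, together with summaries of the continuous outcomes. Under Milestone 2, which waits for 100 initiators in each group, Tables 4, 5 and 7 each carry an Overall column beside Mono and Combo. Table 6 holds the binary outcomes. For these the text says: "We will provide comparisons of response rates between groups with 95% CIs". The shell's columns are Mono, Combo and Mono vs Combo. The rule that missing values and discontinuations count as non-response is stated only in the Table 6 paragraph.

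**The concern.** Table 7 takes up the continuous half of Table 3 on the later cohort, overall and by group. The binary half of Table 3 has no such counterpart, and no reason is given for the difference.

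The overall response rates would then describe the patients available at the first cut, while the stratified rates and the overall continuous changes describe a larger cohort. On a single cohort under a single rule, the overall rate is a weighted average of the two stratum rates and must lie between them. Across two cohorts, or two missing-data rules, that is no longer guaranteed. Objective 1 would also be estimated less precisely than the data in hand allow.

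**Working it through.** **Where each overall result appears**

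| Result | Milestone 1, overall | Milestone 2, overall |
|---|---|---|
| Baseline characteristics | Table 1 | Table 4 |
| Therapy status | Table 2 | Table 5 |
| Continuous outcomes (16 rows) | Table 3 | Table 7 |
| Binary outcomes (7 rows) | Table 3 | none (Table 6: Mono, Combo, difference) |

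**Inputs**
- First cut: size not given. Proxy from the SAP feasibility table (October 2021): 59 monotherapy + 55 combination = 114 patients with a six-month visit.
- Lower alternative: 93, from Protocol 9.5 (October 2020), where "there are 160 tofacitinib initiators within the CorEvitas registry of whom 93 have a 6 month follow-up visit".
- Final cohort: 2 × 73 = 146 (current protocol threshold), 2 × 80 = 160 (the previous one) or 2 × 100 = 200 (SAP threshold). This assumes that both groups stop exactly at the threshold and that the threshold counts patients with a six-month visit.

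**The plan's own precision figure**

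Half-width of the 95% CI by the normal approximation: 1.96 × √(p(1−p)/n). At p = 0.5, n = 80 gives 10.96 points, which meets the stated limit of 11; n = 73 gives 11.47, which does not. The formula is therefore the plan's, at the sample size for which its claim holds. The present point does not depend on this limit.

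**Share of the final cohort absent from the overall binary rates**
- 114 against 146: 32/146 = 21.9%
- 114 against 160: 46/160 = 28.75%
- 114 against 200: 86/200 = 43.0%
- 93 against 146: 53/146 = 36.3%
- 93 against 200: 107/200 = 53.5%

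**Worst-case half-width of the overall rate (p = 0.5)**
- n = 114: 1.96 × √(0.25/114) = 9.18 points
- n = 146: 1.96 × √(0.25/146) = 8.11 points
- n = 160: 7.75 points
- n = 200: 6.93 points

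The loss is 9.18 − 8.11 = 1.07 to 9.18 − 6.93 = 2.25 points.

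**Shift in the estimate**

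The early-cohort rate differs from the full-cohort rate by (share absent) × (difference between early and later patients). The documents give no such difference. If it were 10 points, the shift would be 0.219 × 10 = 2.2 points (146) or 0.43 × 10 = 4.3 points (200).

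**Denominators**

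The SAP restricts six of the seven binary outcomes to patients not already in the target state at baseline. The fourth group of numbers above therefore applies before that restriction; for those six outcomes the denominators are smaller and the half-widths, at the same p, are wider.

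**The case against.** The strongest reply is that this is silence, not a decision. The eligibility criteria have a start date and no end date, the Milestone 2 Overall columns carry the whole cohort forward, and the final report's contents are left open. All of this stands. A reader might infer that the cohort for objective 1 is closed at the first cut, or that the final report must print the early rates. The documents support neither: later patients do enter the overall results for all 16 continuous outcomes, and nothing forbids a re-run of Table 3. What remains is that no re-run is planned.

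Second, the Table 6 shell is weak evidence. Its footnote describes an odds ratio for which no column appears, so the shell may be incomplete or damaged in extraction. But the Milestone 2 text also describes only rates by group and their comparison, so the gap does not rest on the shell alone.

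Third, Protocol 9.7 promises counts for categorical endpoints by treatment group, and the two groups make up the eligible cohort, so a reader could pool them. This helps in part. Table 6 shows rates without n/N, the denominators vary by outcome, and counts to be pooled by the reader are not a planned overall rate with a confidence interval.

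Fourth, 9.2 points is already inside the protocol's limit of 11, and the first output is called interim. Both are true. The precision loss is modest, and staged reporting is a reasonable choice for an estimation study; being called interim does not supply the later estimate.

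**Conclusion.** The point holds for the overall binary outcomes and no further. As written, the plan gives no overall response rate on the cohort used for the stratified rates and for the refreshed overall results, and it leaves open whether Table 3 and Table 6 share a missing-data rule.

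The size is illustrative. It rests on the October 2021 count standing in for the first cut and on a final cohort of 146 to 200: about 22% to 43% of patients absent, and 1.1 to 2.3 points of half-width lost. It is tempting to read 32 omitted patients as a minimum. It is not, because a larger first cut would omit fewer. Nor do the documents show that later patients respond differently, so a biased overall rate is a possibility only. This is an improvement available at almost no cost, not an error that undermines the study.

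**What to change.** Either of two changes is enough:

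- Add an Overall column to the binary part of Table 6, with n/N and a 95% CI for each outcome, and show n/N for Mono and Combo as well; or
- State in Protocol 9.5 and SAP Milestone 2 that Table 3 is re-run on the final data cut, under the same response definitions and non-response imputation as Table 6.

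In both cases, name the result on the final cut as the definitive answer to objective 1 and the Interim Report 1 rates as preliminary. State which missing-data rule the Milestone 1 version of Table 3 follows.

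The cost is one table column or one re-run of an existing program, plus a sentence in each document. It needs no new data and no extra patients.
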